#### **4.D. Enrollment of patients**

For patients who have an elevated BP at a primary care encounter (nurse or provider) but do not yet meet the study's high BP criteria for two consecutive qualifying visits, providers and clinic staff are encouraged to use a standardized hypertension referral order that facilitates scheduling a BP follow up with a provider of their choice (nurse, primary care provider, MTM pharmacist, or specialist).

If the patient meets all study inclusion and exclusion criteria, the patient will be identified automatically upon BP entry through algorithms within a web-service and flagged as "eligible" for Hyperlink. The MA will receive a best practice alert (BPA) that if accepted will open an order for hypertension follow up. The MA will "pend" this order for the provider. Once pended, the order can be removed or signed, but must be addressed by the provider before the encounter can be closed. The follow-up BP order contains defaults to nurse, PCP, or MTM as dictated by appropriate clinic-based care or telehealth care depending on the clinic assignment (see section 5 on Interventions.) The defaults can be modified by the provider prior to signing order using their professional judgement. Once the order is signed and the encounter is closed, the patient is flagged as "enrolled" in the study.

Enrollment will occur in two phases, Vanguard and Main Trial. Vanguard Phase enrollment will begin at the start of Year 2 with 2-4 Vanguard clinics to test procedures and make adjustments so that they are running smoothly. Enrollment of patients will continue until the study sample of 2000 eligible patients has been enrolled in the main trial from the 20 study clinics (Figure 1). In order to avoid very unequal distribution of cluster sizes, enrollment will continue for each clinic until a cap is met (e.g., 200 in a large clinic) or until a minimum is met (e.g., 40 in a small clinic). An average-sized clinic would need to enroll about 8-10 patients per month (or 2-3 patients per week) over 12 months to achieve our sample size.

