### **5.A.2. Hypertension care processes**

The study will create and enhance automated EHR tools to promote the following iterative process:

1. Recognition of uncontrolled BP and high BP study criteria at primary care encounters
2. Therapeutic action to address uncontrolled BP at primary care encounters (may include medication adjustment, addressing non-adherence, and counseling on lifestyle changes)
3. Follow-up visits to re-assess uncontrolled BP within 2-4 weeks. Follow-up visits may be scheduled with a PCP, MA, or MTM pharmacist.

Blood pressure in the ambulatory primary care setting at HealthPartners is measured by the MA during the rooming process for a clinic appointment, or at the time of a nurse blood pressure check using an electronic, automated monitor. If an initial BP  $\geq 140/90$  is entered into the EHR vital signs field it will trigger an automated BPA pop up to remind the MA to repeat the BP if the initial BP is elevated after 5 minutes of rest. If the study inclusion/exclusion criteria are met on the repeat BP, a new BPA appears on the computer screen prompting the MA to open and pend an order for hypertension follow up. The default follow-up interval is 2 weeks unless the BP is  $\geq 180/110$  in which case the default follow up interval is set to 1 week. The type of provider for the follow up visits defaults to nurse, PCP, or MTM depending on the clinic randomization. All defaults can be changed by the MA or at provider discretion if desired by clicking a different options within the order, but the patient is enrolled by any signed order.

Implementation and fidelity to hypertension care processes will be measured as described in Section 7.D and Table 2 using EHR vital sign, diagnosis, current medications, medication order, and encounter data stored and linked to individual study patient IDs and encounters. The study will foster reliable processes in all study clinics through training, measurement, and feedback to improve the consistency with which the hypertension follow up orders are pending, signed, scheduled, and completed.

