## **10. Analysis**

## 10.A Aim 1 Primary and Secondary Analyses

The Aim 1 hypotheses pertain to the effectiveness of telehealth care, predicting that, relative to clinic-based care, it will improve SBP by a practically meaningful 5 mm Hg after 12 months of follow up (H1.1) and patient-reported outcomes (PRO) after 6 months of follow up (H1.2). H1.1 will be tested using random coefficients models in which post-enrollment SBP values will be predicted from clinic-randomized treatment group (Telehealth), time elapsed from enrollment to the SBP (YEARS), and the treatment by time interaction. The most basic form of the H1.1 model will be:

$$SBP_{ij} = \gamma_{00} + \gamma_{10} \text{Telehealth}_i + \gamma_{01} \text{YEARS}_j + \gamma_{11} \text{Telehealth}_i * \text{YEARS}_j + [u_{i0} + e_{ij}],$$

where EHR-derived SBP values documented at all qualifying encounters for 24 months will vary randomly across randomized clinics ( $u_{i0}$ ) and time ( $e_{ij}$ ). Enrolled patients will be assigned to the treatment group to which their clinic is randomly assigned, regardless of their adherence to any component of the clinic-based care or telehealth care approaches. YEARS will be scaled so that 0 represents the date of the primary care encounter at which the patient was enrolled in the study and 1 represents 365 days later. Parameter  $\gamma_{01}$  will therefore estimate the annual rate of change in SBP among clinic-based care patients, and parameter  $\gamma_{11}$  will estimate the difference in rate of SBP change among telehealth relative to clinic-based care patients. The H1.1 model will be adapted for H1.2 by replacing the YEARS component of  $\gamma_{01}$  and  $\gamma_{11}$  with a dummy indicator (6M) for whether the PRO is an enrollment or 6-month survey response.

SBP and PRO are expected to be approximately normally distributed, although the suitability of alternate error distributions and link functions will be assessed if their distributions depart from expectations. Should we observe an imbalance between study groups in the characteristics of randomized clinics, particularly in factors that moderate the fidelity with which the care models may be implemented, we may include clinic-level variables (e.g., % patients >65) as covariates or treatment modifiers, as appropriate.

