### 10.A.2. Per Protocol Analysis Plan

Given the pragmatic, unblinded, cluster-randomized study design, there is potential in this study for otherwise-eligible patients to not be enrolled, and for enrolled patients to subsequently seek treatment interventions (including no treatment) outside of their assigned protocol. Furthermore, we would like to know what the impact of actual receipt of the intervention (as opposed to clinic-level assignment) has on study outcomes. Therefore it will be desirable to conduct a per-protocol analysis (average effect of telehealth vs. best practice, had everyone followed the trial protocol) to complement the intention to treat (ITT) results of the primary analysis. Preliminary data suggests that the ITT approach in this study may be subject to bias due to 1) differential likelihood of enrollment based on provider knowledge of treatment assignment, and/or 2) differential self-selection of patients following through with the assigned treatment intervention. Because these processes operate post-randomization, the randomization scheme cannot ensure confounder balance by enrollment or treatment status, and the study population can be considered as analogous to an observational cohort.

Directed acyclic graphs (DAGs) have been used to depict causal relationships and illustrate potential sources of bias in epidemiologic studies. Briefly, DAGs consist of nodes (e.g., treatment, outcome, other variables) presented in temporal sequence and connected by arrows, which indicate potential causal pathways. If there is no arrow connecting two nodes, it can be assumed that no causal relationship exists. Where 'backdoor' paths can be identified, estimation of causal effects may be biased For this study a DAG might be drawn as depicted in Figure 1, where:

- **Z** is randomized treatment assignment;
- **S=1** represents selection (enrollment) into the study;
- **A** is actual treatment receipt (patient adherence to assigned intervention);
- **Y** represents BP-related study outcomes;
- **L** is a vector of observed patient prognostic factors (e.g., age, comorbidities);
- **U** represents a vector of (possibly unmeasured) patient characteristics predictive of adherence to the assigned intervention protocol.

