## **14. Human Subjects Protection**

### **14.A. Protected Health Information and sources of data**

All necessary data to determine study eligibility, conduct the study interventions, and test the study hypotheses among n=2000 enrolled patients are derived from (a) the EHR, (b) health plan pharmacy claims, and (c) surveys of eligible patients in both study arms. Limited EHR data will include demographics, vital signs, orders, diagnoses, encounters, and laboratory data for specified periods.

Among a smaller group of consenting participants, we will collect focus group data on their experiences receiving BP care. Additional qualitative data will be collected using field observations in clinics, short surveys and interviews with

pharmacists and physicians. These data will be used to assess the impact of study interventions on outcomes. A detailed description of the inclusion and exclusion criteria for study subjects can be found in section 4.c. We anticipate accessing up to 5000 patient records to achieve n=2000 enrolled patients.

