## 2. Patient enrollment/accrual

2.1 Patient enrollment status. The population of interest is patients meeting high BP study criteria cared for by HealthPartners PCPs at 20 representative primary care study clinics. Very few exclusion criteria are in place to maximize the likelihood that study findings are applicable to the population of interest.

We will monitor the characteristics of three patient groups for departures of the study sample from the population of interest. “Registry eligible” patients are adult patients with a hypertension diagnosis and elevated blood pressure at the time they sought care in a HealthPartners primary care clinic. “Hyperlink eligible” patients are the subset of registry eligible patients who also meet study eligibility criteria. A key tool that the study uses to track enrollment and initiate the study interventions is a modified version of an existing “hypertension follow-up order”. This order will be automatically generated and populated with default values appropriate to each treatment group for Hyperlink eligible patients. Accordingly, the “Hyperlink enrolled” patients are the subset of Hyperlink eligible patients whose provider signed a condition-appropriate hypertension follow-up order initiated by the study. The follow-up order only needs to be signed by the provider, not necessarily completed by the patient, to be Hyperlink enrolled.

We will rely on Clarity data to identify and characterize patients from all randomized clinics who fall into each of these three categories. The Hyperlink algorithms gather Clarity data to calculate and store the fields needed to identify registry eligible and Hyperlink eligible patients. Some of these fields will be joined with data from a separate Clarity extract to identify Hyperlink enrolled patients and characterize patients in all three categories.

2.2 Patient enrollment. Hyperlink patient enrollment will begin in the vanguard clinics in August, 2017, and in all 20 clinics for main trial beginning in November, 2017. The study timeline accommodates an 18 month enrollment period so that the last Hyperlink patient would enroll in March, 2019. The total targeted main trial enrollment across the 20 clinics is N=2000.

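### The primary analysis called ITT covers only patients whose unblinded provider signed an order after the clinic's arm was known, and the plan's correction for that selection is specified only for the per-protocol effect

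*Combined protocol and SAP*

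**What the plan says.** **Entry.** Section 4.D has the medical assistant pend an order after an alert. Then: "Once pended, the order can be removed or signed, but must be addressed by the provider before the encounter can be closed". The arm is visible at that moment: "The follow-up BP order contains defaults to nurse, PCP, or MTM as dictated by appropriate clinic-based care or telehealth care", according to the clinic's assignment. Enrollment follows the signature: "Once the order is signed and the encounter is closed, the patient is flagged as" enrolled.

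**Primary population.** Section 7.A takes SBP from enrolled patients. Section 10.A states: "Enrolled patients will be assigned to the treatment group to which their clinic is randomly assigned", whatever their adherence. Section 10.A.2 calls the primary result ITT.

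**Acknowledged problem.** Section 10.A.2 says: "Preliminary data suggests that the ITT approach in this study may be subject to bias due to 1) differential likelihood of enrollment" according to the provider's knowledge of assignment, and/or through patients' self-selection in following through. It adds that randomization cannot guarantee balance by enrollment status, and it likens the study population to an observational cohort.

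**Where the remedy goes.** In the same section, the combined enrollment and adherence weights are applied to a model restricted to patients who followed their assigned protocol. The bias analyses and bounds are likewise for the per-protocol effect.

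**Definition of enrolled.** Section 5.A.2 lets defaults be changed, "but the patient is enrolled by any signed order". Section 15, item 2.1, describes the enrolled as the "subset of Hyperlink eligible patients whose provider signed a condition-appropriate hypertension follow-up order initiated by the study".

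**The concern.** Following the clinic's arm regardless of adherence protects against bias after entry, but not against bias at entry. Here entry is a decision made after randomization by someone who knows the arm. If signing depends on both the arm and the patient's prognosis, conditioning on enrollment links assignment to prognosis. Section 10.A.2 traces this path (conditioning on the collider S, then through L) for the effect of treatment received. The same conditioning reaches the effect of assignment, which is what H1.1 estimates.

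At stake is the main claim of the trial. A difference in SBP trend could partly reflect which patients providers referred in each arm. The plan raises this doubt and will build an enrollment model, but does not use that model on the result in doubt.

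**Working it through.** **1. What binds the primary model.**
- Section 10.A: clinic-level covariates may be added if clinic characteristics are imbalanced. This is optional and not at patient level.
- Section 10.A.1: the models can be adapted for patient covariates and for sensitivity analyses, with subgroup effects as the main use. No selection correction is specified.
- Section 15, items 2.2 and 4.1: progression from eligible to enrolled is monitored by arm and clinic, and covariate balance is checked to inform the primary analyses. No action is attached.
- Section 10.A.2: enrollment weights, bias analyses and bounds, all for the per-protocol effect.

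**2. Which parameter is exposed.** H1.1 tests γ11, the arm-by-time slope. A constant difference in SBP level between arms goes into γ10. So γ11 is biased only if arm-differential selection is related to the course of SBP, for example through regression to the mean. Section 10.A.3 shows why this is plausible: mean SBP was 159.9 at the index visit and 150.7 over all readings, a gap of 159.9 − 150.7 = 9.2 mm Hg.

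**3. The plan's own figure.** Inputs from section 10.A.3: 20 clinics of 100 patients, 3 SBP values over 24 months, clinic ICC .01 to .03, SD 20.4, 80% power, two-sided 5%. I assumed readings at years 0, 1 and 2, so Sxx = 2.

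MDSE = (1.960 + 0.842) × √[2 × (1 + 99 × ICC) × (1 − ICC) / (1000 × 2)]
- ICC .01: 0.1244
- ICC .03: 0.1739

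The stated .124 and .174 reproduce, and 20.4 × .124 = 2.53 and 20.4 × .174 = 3.55 mm Hg. The power figure is not in error; it makes no allowance for selection.

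**4. Illustrative bias.** Every input except 20.4 is assumed. In a normal selection model with enrolled share p, the mean of the latent enrollment tendency among the enrolled is λ(p) = φ(z)/p, where z cuts off the upper share p. Then bias = r × 20.4 × [λ(lower share) − λ(higher share)], where r is the correlation between that tendency and 12-month SBP change. The 20.4 is the SD of all SBP values, standing in for the SD of change, which is not given; the bias scales with it.

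| Enrolled shares by arm | λ difference | r = .1 | r = .2 | r = .3 |
|---|---|---|---|---|
| 45% v 35% | 1.058 − 0.880 = 0.179 | 0.36 | 0.73 | 1.09 |
| 50% v 30% | 1.159 − 0.798 = 0.361 | 0.74 | 1.47 | 2.21 |
| 60% v 30% | 1.159 − 0.644 = 0.515 | 1.05 | 2.10 | 3.15 |

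Equal shares with the same r give zero.

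**5. Effect on the test.** The implied standard errors are 2.53/2.802 = 0.90 and 3.55/2.802 = 1.27 mm Hg. A bias of 1.47 mm Hg would raise the two-sided type I error from 5% to about 37% (ICC .01) or 21% (ICC .03).

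**6. Precision after weighting.** Suppose the weights inflate variance by 1.25 to 2.0 (assumed), so that the effective clinic size is 100 divided by that factor. The detectable difference becomes 2.69 to 3.10 mm Hg (ICC .01) or 3.65 to 3.96 (ICC .03). Power for 5 mm Hg stays at 94% or more.

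**7. All eligible patients.** Assume about 5,000 eligible, 250 per clinic. The detectable difference is about 2.1 mm Hg (ICC .01) to 3.3 (ICC .03). If patients who are not enrolled gain nothing, a 5 mm Hg effect is diluted:
- 80% enrolled (assumed): 4 mm Hg, power 93% to over 99%
- 60%: 3 mm Hg, power 73% to 98%
- 40%: 2 mm Hg, power 40% to 75%

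**The case against.** The best defence is that the plan is open about the problem, monitors it by arm and clinic, checks balance before the primary analysis, and says the models can be adapted. It also hedges: the text says the result may be biased, and joins its two reasons with and/or. The second reason, follow-through after enrollment, does not by itself bias a comparison by assignment. All of this stands, but none of it commits the sponsor to correct or qualify the primary result.

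Four stronger readings are tempting, and the documents do not support them.
- **That the preliminary data show the primary result is biased.** They are said only to suggest that it may be.
- **That 40% of eligible patients are enrolled.** Section 14.A says: "We anticipate accessing up to 5000 patient records to achieve n=2000 enrolled patients". This is a ceiling on record access, and nothing says those records all belong to eligible patients.
- **That a 0.1 to 0.2 SD shift in prognosis, times 20.4, gives a bias of 2.0 to 4.1 mm Hg.** That is a shift in level, which γ10 absorbs if it is constant.
- **That the wording in section 15 drops telehealth patients whose default was changed.** It may simply mean the arm's version of the study order. The same item says the order need only be signed, and section 5.A.2 enrolls on any signed order. It is an ambiguity, not a demonstrated exclusion.

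The remedy also has limits. Weighting needs no unmeasured confounding, which section 10.A.2 itself calls untestable. The all-eligible set is not fully protected either, because eligibility rests on a repeat BP taken by unblinded staff (sections 4.C and 5.A.2).

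**Conclusion.** The point holds in this form: H1.1 is an analysis by clinic assignment of a set selected after randomization with knowledge of the arm. The plan names the resulting risk but specifies a correction only for a different estimand. Neither the direction nor the size of any bias can be found from the documents. The range in step 4 shows that moderate, arm-differential selection related to SBP change could reach the order of the detectable difference. It rests on assumed shares and correlations, the same selection mechanism in both arms, and the pooled SD as a stand-in. It is not an estimate of what will happen in this trial.

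**What to change.** 1. Pre-specify H1.1 with the enrollment weights alone, leaving out the adherence weights, and adjust for pre-enrollment patient covariates. Use SBP from the earlier qualifying encounter as a covariate only if it is not also an outcome row. Section 7.A extracts SBP at both qualifying encounters and section 10.A sets time zero at enrollment, so the SAP should state which readings are outcomes.
2. Pre-specify the same model on all Hyperlink-eligible patients by clinic arm, indexed at the first eligible main-trial encounter, and report it beside the enrolled-patient result. The two answer different questions, so neither should replace the other. Describe the unweighted result as an analysis of enrolled patients by clinic assignment, not as ITT without qualification. Align section 10.A.3, which speaks of eligible patients, with section 10.A, which speaks of enrolled ones.
3. Reconcile sections 5.A.2 and 15 (item 2.1) so that patients whose order defaults were changed are clearly retained.

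**Cost.** Mostly SAP wording. The enrollment model already needs data on eligible patients who were not enrolled, and section 15, item 2.1, plans to identify and characterize them. Their follow-up SBP would have to be extracted, and the waiver in section 14.C.1.a confirmed to cover it, since section 14.A frames hypothesis testing around the 2,000 enrolled. The price in precision and dilution is in steps 6 and 7.

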**Figure 1. Directed acyclic graph representing the primary study aims.**

For the per-protocol analysis, we are interested in estimating the effect of **A** on **Y** (as opposed to the ITT effect of randomized assignment **Z** on **Y**). The DAG above shows multiple backdoor paths from **A** to **Y**: 1) through **L**, 2) through conditioning on the collider **S** and then through **L**, and 3) through **U**. To account for these sources of potential bias, we will use inverse probability weighting to estimate the per-protocol effect of the telehealth intervention on blood pressure outcomes.

Inverse probability weighting can be used to estimate unbiased measures of effect where selection bias or confounding is present, under specific assumptions. To estimate the per-protocol effect of the telehealth intervention on BP

outcomes, we will use a two-stage modeling process. In the first stage, we will construct logistic regression models for 1) enrollment, and 2) patient adherence to the assigned treatment. Candidate variables for inclusion in these models will be specified *a priori*; from these candidate variables, models will be optimized using Lasso selection based on the Bayesian Information Criterion. Individual probabilities of enrollment/adherence can then be calculated based on each patient's vector of covariate values. Stabilized inverse probability weights will then be calculated, combined (enrollment IPW \* adherence IPW), and diagnostically evaluated as previously described.

Based on contextual knowledge and preliminary summaries of the study population, we anticipate that the variables listed in Table 1 (in addition to clinic assignment of telehealth vs. best practice) may be associated with enrollment and/or treatment adherence. All will be considered for model inclusion. Patient-reported outcome measures (PROMs) will be available only for patients who are enrolled (and complete a survey), thus, these will be considered for the patient adherence model, but not the model for enrollment.

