**Table 1. Candidate Covariates for Inverse Probability Weight Models for Enrollment and Adherence**

Demographics	Comorbidities	Labs / Vital Signs	Other	Survey PROMs

 
▪ Age
 
▪ Gender
 
▪ Insurance Status
 
▪ Race/Ethnicity
 
▪ SES
 
▪ Primary Language
 
	
 
▪ Comorbidity Index (e.g., Charlson, Elixhauser)
 
▪ CVD/CHD
 
▪ CV Risk Score
 
▪ Smoking
 
	
 
▪ Baseline BP
 
▪ BMI
 
▪ eGFR
 
▪ Creatinine
 
	
 
▪ BP Meds
 
▪ Med Count
 
▪ Utilization
 
▪ Clinical characteristics (e.g., % BP control)
 
▪ Provider characteristics (e.g., Specialty)
 
▪ Calendar time
 
	
 
▪ Self-Rated Health
 
▪ Prior BP Monitoring
 
▪ Education
 
▪ Employment
 
▪ Life Satisfaction
 
▪ Self-Efficacy
 

In the second stage of analysis we will apply the weights to generalized linear regression models to estimate the effect of per-protocol treatment on study outcomes. This model will be restricted to study patients who followed their assigned protocol (MTM visit if intervention, no MTM visit if best practice). By weighting individuals by their inverse probability of enrollment/adherence, we essentially create a pseudo-population for analysis, in which factors that were unbalanced in those who were enrolled/adherent vs. those who were not are no longer unbalanced. The effect estimate from this weighted model then represents the unbiased effect of actual, per-protocol treatment on BP outcomes.

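### The per-protocol adherence weights are not specified by arm, although adherence is coded in opposite directions in the two arms, so they can leave much of the measured confounding in place

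*Combined protocol and SAP*

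**What the plan says.** The per-protocol plan in section 10.A.2 has two stages. For the weights, "In the first stage, we will construct logistic regression models for 1) enrollment, and 2) patient adherence to the assigned treatment". Assignment appears in the list of candidates: "we anticipate that the variables listed in Table 1 (in addition to clinic assignment of telehealth vs. best practice) may be associated" with enrollment or adherence. From those candidates, "models will be optimized using Lasso selection based on the Bayesian Information Criterion". The text on survey measures refers to adherence in the singular: "these will be considered for the patient adherence model, but not the model for enrollment".

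The outcome stage keeps only patients who followed their assignment, that is, "MTM visit if intervention, no MTM visit if best practice". The plan expects the weights to produce a population in which "factors that were unbalanced in those who were enrolled/adherent vs. those who were not are no longer unbalanced", and describes the resulting estimate as the unbiased effect of treatment as received.

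No arm-specific weight model and no arm-by-covariate term is named. The covariate interactions in section 10.A.1 belong to the H1 outcome models.

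**The concern.** The dependent variable of the adherence model changes meaning with arm. An MTM visit is adherence in telehealth and non-adherence in clinic-based care. Both can occur, because sections 5.A.1 and 5.A.2 make MTM visits available in clinic-based care.

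Take a factor that makes an MTM visit more likely in either arm, for example higher BP or more drugs. It raises adherence in telehealth and lowers it in clinic-based care. A single coefficient cannot represent both effects, so the weights under-adjust for that factor even though it is measured and in the candidate list.

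This matters because section 10.A.2 says preliminary data suggest that the ITT comparison may be biased by selection after randomization. Readers will therefore lean on the per-protocol estimate.

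**Working it through.** The plan gives no figure for these weights, so there is none to reproduce. The check asks what a pooled main-effects model does to one measured confounder.

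**Inputs.** From the documents: the definition of adherence, the restriction to adherent patients, stabilized weights, and a true effect of -5 mm Hg (the anticipated effect). Assumed, because the documents give none: MTM visit rates, the log odds ratio of an MTM visit per SD of a standardized covariate L, and 4 mm Hg of SBP per SD of L.

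**Step 1: signs.** Let logit P(MTM visit) = a1 + b1·L in telehealth and a0 + b0·L in clinic-based care. Then logit P(adherent) = a1 + b1·L in telehealth and -a0 - b0·L in clinic-based care. With b1 = b0 = b, the adherence slopes are +b and -b.

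**Step 2: the pooled coefficient.** With arm and L as main effects, the coefficient of L is approximately an information-weighted average:

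γ ≈ (I1·b1 - I0·b0) / (I1 + I0), where I is roughly p(1 - p) for the MTM rate p in that arm.

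- MTM rates 60% and 20%, b = ln 2 = 0.69: I1 = 0.24, I0 = 0.16, γ ≈ (0.08/0.40) × 0.69 = 0.14. The large-sample fit gives 0.12, against true values of +0.69 and -0.69.
- Rates 70% and 30%: I1 = I0 = 0.21, γ = 0. The weights ignore L.
- Rates 60% and 5%: I1 = 0.24, I0 = 0.0475, γ ≈ (0.1925/0.2875) × 0.69 = 0.46. The telehealth arm dominates and the cancellation is only partial.

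**Step 3: effect on the estimate.** The bias is 4 × (weighted mean of L in adherent telehealth patients minus that in adherent clinic-based patients). At 60%/20%, the unweighted estimate is -3.48 (bias 1.52), pooled weights give -3.56 (bias 1.44), and arm-specific weights give -5.00. So 1.44/1.52 = 95% of the bias is left.

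**Step 4: other inputs.** Large-sample simulation, with numerical integration agreeing to about one percentage point:

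| MTM visit, telehealth / clinic-based | Log OR for MTM visit, telehealth / clinic-based | Share of bias left, pooled weights |
|---|---|---|
| 70% / 30% | 0.5 / 0.5 or 1.0 / 1.0 | 100% |
| 50% / 30% | 0.69 / 0.69 | 98% |
| 60% / 20% | 0.69 / 0.69 | 95% |
| 80% / 5% | 0.69 / 0.69 | 72% |
| 60% / 5% | 0.69 / 0.69 | 54% |
| 60% / 2% | 0.69 / 0.69 | 28% |
| 60% / 20% | 0.69 / 0 | 76% |
| 60% / 10% | 0.69 / 0 | 53% |
| 60% / 10% | 0.69 / -0.3 | 35% |
| 60% / 10% | 0.69 / -0.69 | 1% |
| 70% / 30% | 1.0 / 0.3 | 105% |

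In the last row but one, L acts on adherence equally in both arms and the pooled model is correct. In the last row, pooled weighting is slightly worse than none. Arm-specific weights gave about -5 in every scenario where some bias was present.

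**Step 5: would the checks show it?** Under the pooled model the mean stabilized weight stayed between 0.98 and 1.00. A mean-weight check would look reassuring.

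**Step 6: selection at trial size.** With 1,000 patients per arm, 25 candidates and Lasso/BIC (60 replicates), pooled selection kept the confounder in 23% of runs at 60%/20%, 97% at 60%/10% and 100% at 60%/5%.

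**The case against.** The strongest reply is that the plan never says pooled or main effects only. It lists candidates and leaves functional form open, so arm interactions remain possible. That stands. The pooled reading is natural, given the singular adherence model and assignment listed beside the other candidates, but it is an inference.

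The plan also attaches conditions. It says inverse probability weighting is unbiased under specific assumptions, names correct model specification among them, promises weight diagnostics and sensitivity analyses, and adds bias analyses and bounds. None of these targets the arm-by-covariate problem. The diagnostics and sensitivity analyses are not described in that detail, re-specification is offered only for positivity violations, and the bias analyses are offered in answer to unmeasured confounding.

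A reader might infer that the effects always cancel and nearly all confounding stays. The documents do not support this, because they give no MTM rates or slopes. They even give a reason for slopes to differ: the follow-up order defaults to the MTM pharmacist in telehealth clinics (section 5.B), whereas a visit in clinic-based care generally needs a referral, a self-referral or a changed default.

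A reader might also infer that Lasso will generally drop these confounders. Step 6 shows that this depends on the MTM rates.

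Finally, a reader might extend the problem to the enrollment model. Enrollment is a signed order in both arms, so there is no opposite coding.

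**Conclusion.** The point holds in limited form. As naturally read, section 10.A.2 specifies a weight model that is wrong for any covariate whose effect on adherence differs by arm, and the definition of adherence makes opposite signs likely. With equal MTM slopes, about 30% to 98% of that covariate's bias remained across the unequal-information scenarios, and all of it where p(1 - p) for the MTM visit was the same in both arms. Unequal slopes usually left less, with one exception, and nothing remained when the covariate acted on adherence equally in both arms.

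In the 60%/20% example the residual is 1.44 mm Hg, against a hypothesized 5 mm Hg and the 2 or 3 mm Hg that section 10.A.3 calls clinically important. These sizes rest on assumed rates, slopes and prognostic strength. The direction of the bias depends on whether the factor raises or lowers SBP.

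The plan's description of the weighted estimate as unbiased does not follow from what is specified. The primary ITT analysis and the H1.2 tests are not affected.

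**What to change.** In section 10.A.2:

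- Model the MTM visit (adherence) separately within each randomized arm and take each patient's weight from their own arm's model. Alternatively, force arm and all arm-by-covariate terms into one model. At present Lasso could even drop arm.
- Stabilize with the arm-specific adherence proportion.
- Force in key confounders such as baseline BP and medication count, and apply Lasso/BIC only to the rest.
- Report weighted covariate balance between the two adherent groups and, within each arm, between adherent and all enrolled patients.

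The cost is a few sentences and one extra model fit. The downside is fewer events per model, hence more variable weights, and possible under-selection in the arm with few non-adherent patients. In the trial-size Lasso/BIC runs, by-arm weights gave -4.57 to -4.66, leaving 0.34 to 0.43 mm Hg of bias. The clinic-based fit missed the true confounder in 15% of runs at a 5% MTM rate. That is why forcing matters.

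By-arm enrollment models are optional. Section 10.A.2 expects enrollment to differ by arm, but the opposite-coding argument does not apply there.

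Section 5.A.2 allows MTM follow-up within clinic-based care while section 10.A.2 counts it as non-adherence. These passages must be reconciled before the adherence variable is built.
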